## **10.9. Analysis of immunogenicity**

The primary analysis will be performed on the PPS for immunogenicity and, if in any study group the percentage of vaccinated subjects with serological results excluded from the PPS for analysis of immunogenicity is at least 10%, a second analysis will be performed on the ES.

**CONFIDENTIAL**208851 (RSV OA=ADJ-002)  
Protocol Amendment 1 Final**10.9.1. Within groups evaluation - humoral immune response**

For each group, at each time point that blood samples are collected for humoral immune response and for each assay (unless otherwise specified):

**In Part A and Part B:**

- Percentage of subjects above pre-defined threshold and their exact 95% CI will be tabulated.
- GMCs/GMTs and their 95% CI will be tabulated and represented graphically.
- Geometric mean of ratios of antibody titer/concentrations at each individual post-vaccination time point over pre-vaccination (Day 1) will be tabulated with 95% CI.
- Antibody titer/concentration will be displayed using reverse cumulative curves.
- The ratio of the RSVPreF3 ELISA antibody concentrations over the RSV-A neutralizing antibody titers will be computed and tabulated using descriptive statistics (Ratio of fold increase Post- over Pre-vaccination).

**In Part B only:**

- The distributions of antibody titers/concentrations will be tabulated.
- Individual post-vaccination results (at Days 31, 61 and 91) versus pre-vaccination results (Day 1) will be plotted using scatter plots. Results of the placebo group will be used as a reference.
- Distribution of the fold increase of the antibody titers/concentrations (post- over pre-vaccination titers) will be tabulated.
- The kinetics of GMT/GMCs will be plotted as a function of time for subjects with results available at all time points.

The immunogenicity analysis will also be performed by age category (60-69 years and 70-80 years) in Part B only. The humoral immune response by CMV status before vaccination might be explored in Parts A and B.

**10.9.2. Within groups evaluation - Cell-mediated immune response**

The following parameters will be summarised by group using descriptive statistics (N, geometric mean [GM], min, Q1, median, Q3, max) at each time point during which blood samples are collected for CMI:

**In Part A and Part B:**

- Frequency of RSVPreF3-specific CD4+ T-cells identified as expressing **at least 2 markers** among IL-2, CD40L, TNF- $\alpha$ , IFN- $\gamma$ , upon in vitro stimulation and background subtracted, measured by ICS using PBMCs.

**CONFIDENTIAL**208851 (RSV OA=ADJ-002)  
Protocol Amendment 1 Final

- Frequency of CD4+ and/or CD8+ T-cells expressing **any combination of immune marker(s)** among CD40L, 41BB, IL-2, TNF- $\alpha$ , IFN- $\gamma$ , IL-13, and IL-17, as measured by ICS using PBMCs.
- Geometric mean ratios of frequency of RSVPreF3-specific CD4+ T-cells identified as expressing **at least 2 marker(s)** among IL-2, CD40L, TNF- $\alpha$ , IFN- $\gamma$ , at each post-vaccination time point over pre-vaccination (Day 1) will be tabulated with 95% CI.

**In Part B only:**

- Frequency of RSVPreF3-specific memory B-cells, as measured by ELISpot using PBMCs.

This will be displayed overall and by pre-vaccination category: <Q1, Q1-Q3, >Q3, where Q1/Q3 are respectively the 25th and the 75th percentiles of the results at pre-vaccination computed on pooled groups.

In addition, vaccine response in terms of RSVPreF3-specific CD4+ T-cells expressing at least 2 markers among IL-2, CD40L, TNF- $\alpha$ , IFN- $\gamma$ , will be explored and summarised by group.

The descriptive immunogenicity analysis will also be performed by age category (60-69 years and 70-80 years) in Part B only. The cell-mediated immune response by CMV status before vaccination might be explored in Parts A and B.

#### **10.9.3. Between groups evaluation (Part B only)**

Statistical analyses will be performed to compare the 9 RSV investigational vaccine formulations in terms of RSV-A neutralizing antibody titers and RSVPreF3-specific CD4+ T-cells at Day 91.

Additional exploratory comparisons might also be performed on the RSVPreF3 ELISA antibody concentrations at Day 91.

The between-groups analysis will be performed in several steps as follows:

1. The 9 RSV formulations will be first compared to the Placebo in order to identify groups whose means are significantly different from the mean of the Placebo group, in terms of RSV-A neutralizing antibody titers at Day 91 (alpha=2.5%, Dunnett's adjustment test for multiplicity).
2. The effect of the second vaccination will be evaluated by comparing the means one month post-Dose 2 (Day 91) and one month post-Dose 1 (Day 31), on the groups pooled according to their adjuvant content (AS01B, AS01E and Plain), in terms of RSVPreF3-specific CD4+ T-cells and RSV-A neutralizing antibody titers.
3. The RSV formulations will be then compared using an ANCOVA model. Appropriate contrasts will be implemented:

**CONFIDENTIAL**208851 (RSV OA=ADJ-002)  
Protocol Amendment 1 Final

- To demonstrate the adjuvant effect (on pooled groups according to their adjuvant content: AS01B, AS01E, Plain), by testing sequentially AS01B and AS01E versus Plain (alpha=2.5% for each test) in terms of CD4+ T-cells expressing at least 2 markers and RSV-A neutralizing antibodies at Day 91 and, if applicable, by comparing AS01B vs AS01E.
- To demonstrate linearity of increase in immune response when increasing the antigen dose in each adjuvanted group in terms of RSV-A neutralizing antibody and/or RSVPreF3-specific CD4+ T-cells at Day 91.

Further ANCOVA t-tests would demonstrate superiority of 120 µg or 60 µg, should a quadratic effect be demonstrated.

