#### **10.4. Determination of sample size**

In Part A, the sample size of 12 subjects per group would provide a probability of 80% or 90% to observe at least one AE, if the true AE rate is 12.6% or 17.5%, respectively.

In Part B, the sample size of 100 subjects per group would provide a probability of 80% or 90% to observe at least one AE, if the true AE rate is 1.6% or 2.3%, respectively.

The study is designed as a factorial design with 2 factors resulting in 9 RSV formulations (~100 subjects per RSV formulation in Part B, Step 1 and Step 2 pooled, referred as “group” in text below) (see [Table 31](#)). In addition, a placebo group will be evaluated (~100 subjects, Step 1 and Step 2 pooled).

**CONFIDENTIAL**208851 (RSV OA=ADJ-002)  
Protocol Amendment 1 Final**Table 31 Factorial design**

		No adjuvant (Plain)	Factor B: Adjuvant	
			AS01 E	AS01 B
Factor A: Antigen dose	30 µg	100	100	100
	60 µg	100	100	100
	120 µg	100	100	100

Considering a 10% rate of non-evaluable subjects, it is assumed that approximately 90 subjects per group will be evaluable for the analysis of RSV-A neutralizing antibody titers and for the CD4+ T-cells response.

The 9 RSV formulations will be first compared to the Placebo in terms of RSV-A neutralizing antibody titers at Day 91 using the Dunnett's method via a one way ANOVA model. The sample size of 90 subjects per group (in 10 groups) achieves  $\geq 90\%$  power to detect a difference of at least 2.3-fold (alpha=0.025, SD=0.4, CV=115.6%, PASS 12.0.10 Multiple comparisons Analysis using Dunnett's adjustment for multiplicity).

The effect of the second vaccination will then be evaluated by comparing the response one month post-Dose 2 (Day 91) and one month post-Dose 1 (Day 31) in terms of RSVPreF3-specific CD4+ T-cells and RSV-A neutralizing antibodies. This comparison will be done on the groups pooled according to their adjuvant content (3 groups of 270 subjects: AS01B, AS01E and Plain). [Table 32](#) below presents the power and fold increase that can be detected with a sample size of 270 subjects per pooled group. The sample size of 270 subjects per group achieves 90% power to detect a difference of at least 1.2 fold between Dose 2 and Dose 1.

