**Table 33 Effect of adjuvant: Power and fold increase with a sample size of 270 subjects per pooled group**

N/group	N evaluable/group	N Pooled groups	Power	Fold increase
100	90	270	90%	1.3
			80%	1.25

Power calculation done in PASS 12.0.10: Two-sample T-test assuming equal variance, with alpha=0.025, SD=0.4 (CV=115.6%).

**CONFIDENTIAL**208851 (RSV OA=ADJ-002)  
Protocol Amendment 1 Final

Finally, the antigen dose-response will be evaluated in each adjuvanted group in terms of RSV-A neutralizing antibody titers and RSVPreF3-specific CD4+ T-cells at Day 91.

**Table 34** below presents the power and fold increase that can be detected with a sample size of 90 per group. The sample size of 90 subjects per group would provide 90% power to detect a difference of at least 1.56 between 2 groups.

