**Table 34 Antigen dose-response: Power and fold increase with a sample size of 90 subjects per group**

N/group	N evaluable/group	Power	Fold increase
100	90	90%	1.56
		85%	1.51
		80%	1.47

Power calculation done in PASS 12.0.10: Two-sample T-test assuming equal variance, with alpha=0.025, SD=0.4 (CV=115.6%).

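### Table 34's 90% power is for an ungated two-dose t-test, but Section 10.9.3 runs the dose-superiority t-tests only after a quadratic effect is shown, so the 90% does not apply to them

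*Protocol*

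**What the plan says.** Section 10.4 assumes 10% non-evaluable subjects, leaving 90 of 100 per group ("Considering a 10% rate of non-evaluable subjects, it is assumed that approximately 90 subjects per group will be evaluable"). For antigen dose it then states: "The sample size of 90 subjects per group would provide 90% power to detect a difference of at least 1.56 between 2 groups". Table 34 is titled "Antigen dose-response: Power and fold increase with a sample size of 90 subjects per group", and its footnote gives the basis as "Two-sample T-test assuming equal variance, with alpha=0.025, SD=0.4 (CV=115.6"%). Sidedness is not stated.

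Section 10.9.3 sets out the analysis. In step 3, "The RSV formulations will be then compared using an ANCOVA model", with contrasts that the text calls appropriate but does not specify. One aim is "To demonstrate linearity of increase in immune response when increasing the antigen dose in each adjuvanted group", for RSV-A neutralizing antibody and/or CD4+ T-cells at Day 91. The t-tests for superiority of 120 µg or 60 µg follow only "should a quadratic effect be demonstrated".

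The section gives no contrast coefficients, no dose scale (log or raw µg), and no alpha for the linear or quadratic contrast. Section 10.4 gives no power for the quadratic contrast or for the two-stage sequence.

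**The concern.** The test that was powered is not the test that will be run. Table 34 treats a comparison of two doses as if it always takes place. Under Section 10.9.3 it takes place only if a curvature test on three groups succeeds first, and that test has a larger standard error for the same step in response.

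The Synopsis and Section 1.2.2 make selection of a formulation the main purpose, resting primarily on RSV-A neutralizing titers and CD4+ T-cells, which are the variables tested here. If the response levels off at 60 µg, or rises only at 120 µg, the pairwise dose tests are what would separate adjacent doses. Those are also the shapes in which the gate often stays shut at the design effect.

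**Working it through.** **Inputs.** From Section 10.4 and Table 34: n = 90 per group, SD = 0.4 (log10), alpha = 0.025, design step 1.56-fold, so d = log10(1.56) = 0.1931. Assumed, because the protocol does not fix them: the dose scores (both codings shown), the alpha of the quadratic contrast (two-sided 5% and 2.5%, critical values 1.96 and 2.24), and no gain from the ANCOVA covariate (varied below).

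**1. The plan's own figure.** SE of a two-group difference = 0.4 × √(2/90) = 0.0596, and z = 0.1931/0.0596 = 3.24. At one-sided 0.025 the power is 89.9% (normal) or 89.6% (t). The 1.51-fold and 1.47-fold rows give 85% and 80%. Table 34 therefore reproduces as an ungated t-test. Two-sided 0.025 gives 84% at 1.56-fold and does not reproduce it.

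**2. Gate with log-dose scores.** The doses double, so log-dose scores are equally spaced and the quadratic contrast is (1, −2, 1). SE = 0.4 × √(6/90) = 0.1033, which is √3 = 1.73 times the pairwise SE. For a plateau (0, d, d) or a rise only at 120 µg (0, 0, d) the absolute contrast is d, so z = 0.1931/0.1033 = 1.87.

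**3. Gate with raw-µg scores.** For 30, 60 and 120 the linear contrast is (−4, −1, 5) and the quadratic is (2, −3, 1). SE = 0.4 × √(14/90) = 0.1578. For the plateau the absolute contrast is 2d, z = 0.3862/0.1578 = 2.45. For a rise only at 120 µg it is d, z = 1.22.

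Chance that the gate opens at a 1.56-fold step:

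| Shape | Scores | Two-sided 5% | Two-sided 2.5% |
|---|---|---|---|
| Plateau from 60 µg | log dose | 46% | 36% |
| Rise only at 120 µg | log dose | 46% | 36% |
| Plateau from 60 µg | raw µg | 69% | 58% |
| Rise only at 120 µg | raw µg | 23% | 15.5% |
| Peak at 60 µg (0, d, 0) | log dose | 96% | 93% |
| Peak at 60 µg (0, d, 0) | raw µg | 96% | 92% |

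The unrounded log-dose figure at 2.5% is 35.5%.

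**4. Gate and t-test together.** For the adjacent pair where the step falls, the joint probability is almost the same as the gate probability: 46%/36% (log) and 69%/58% (raw) for 60 versus 30 µg on a plateau. For 120 versus 30 µg on the same plateau it is 42%/32% (log) and 63%/54% (raw). For a peak at 60 µg, 60 versus 30 µg keeps 88-90%.

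**5. Step needed.** For the log-dose quadratic contrast to have 90% power on a plateau, the step must be 10^((1.96 + 1.28) × 0.1033) = 2.16-fold, or 2.31-fold at two-sided 2.5%.

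**6. Covariate gain.** With an assumed baseline correlation of 0.5 the SD falls to 0.4 × √0.75 = 0.346. The plateau gate becomes 47-58% (log) or 72-81% (raw). At 0.7 it is 65-75% (log) or 88-93% (raw). The ungated test gains from the same smaller SD.

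**7. An alternative gate.** Simulating a 5% 2-df test of dose followed by the pairwise test gives 87.5% at 1.56-fold for a plateau or a top-dose-only step, and about 90% at 1.59-fold. For 120 versus 30 µg at 1.56-fold overall it gives about 82% under a log-linear rise and 84% for a partial plateau (0, 0.75d, d).

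**The case against.** Table 34 is titled for the antigen dose-response and is not tied by name to the follow-up t-tests. With equally spaced scores the linear contrast is (−1, 0, 1), which is exactly 120 versus 30 µg, so 90% at 1.56-fold is right for the ungated first test. That stands. It leaves the adjacent-dose comparisons without a power statement that fits the way they are reached.

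A reader might infer that the real power is simply 35-46%. The document does not support that as a single figure. It assumes log-dose scores, a 1.56-fold step of one particular shape and no covariate gain, and other shapes and codings give anything from a few per cent to about 90%. Coefficients may properly sit in the SAP, so leaving them open is not itself a fault.

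A reader might also infer that a plateau will be declared linear about half the time. The chance of a significant linear and non-significant quadratic contrast on a plateau is 48-54% with log scores but 25-30% with raw scores. The protocol never says that a non-significant quadratic term leads to a claim of linearity. Such a result should not be read as evidence of linearity, but the rule is the reader's and not the document's.

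Section 10.11 calls the analyses descriptive and the comparisons exploratory, the primary objective is safety, and group means will be tabulated and plotted in any case, so a plateau could still be seen. This limits the consequence. The caution in Section 10.11, however, is about unadjusted multiplicity of endpoints. It does not address a power figure attached to a test that is run only conditionally.

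**Conclusion.** The point holds in this form: the 90% in Table 34 does not apply to the 60 and 120 µg superiority t-tests as Section 10.9.3 conditions them. With n = 90, SD 0.4, no covariate gain, quadratic alpha between two-sided 2.5% and 5%, and a 1.56-fold step, the gate opens about 35-46% of the time with log-dose scores. With raw-µg scores it opens 58-69% (plateau) or 16-23% (rise only at 120 µg). The 90% remains valid for the 120 versus 30 µg linear contrast with equally spaced scores, and approximately for a response peaking at 60 µg. A strong baseline covariate would narrow the shortfall, but the protocol gives no correlation to rely on.

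**What to change.** In Section 10.9.3, remove the quadratic effect as the condition for the pairwise dose tests. Report the three pairwise ANCOVA contrasts within each adjuvant group, for example after a significant 2-df test of dose, and keep the linear and quadratic estimates with confidence intervals as description.

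Restate Table 34 for the procedure chosen. With the 2-df gate this is about 88% at 1.56-fold for a plateau or top-dose-only step, and about 82% for 120 versus 30 µg under a log-linear rise. The shape should be named beside each figure.

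If the quadratic gate is kept, say that Table 34 does not cover the gated t-tests, and give their power with the dose scores and alpha assumed.

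The cost is wording in Section 10.9.3, a revised Table 34 and a slightly lower stated power. No extra subjects or data are needed.

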### **10.10. Analysis of RTI for Part B**

The analysis will be performed on the ES.

Any RTI episode for which a visit for the assessment of potential RSV-RTI has been performed (with nasal/throat swab sampling) will be considered for the analysis. The assessment of RSV infection will be performed using qRT-PCR on nasal/throat swabs separately for samples collected by the subject and those collected by an appropriately qualified person (i.e., medical or nursing) at the assessment visit.

The proportion of subjects with at least one RSV-associated RTI (with 95 % CI) will be calculated by group.

Descriptive analyses (mean, median, min, max) of viral load assessed by quantitative PCR (RSV-A/B) of RSV-RTI will be performed by study group.

The incidence rate of all-cause RTI (with 95% CI) will be calculated by group. These will also be presented by co-infection identified by multiplex PCR.

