## RSV molecular biology

For identified RTI cases under active or passive surveillance, the potential RSV infection will be assessed by quantitative reverse transcription PCR (qRT-PCR) testing of nasal/throat swab specimen (see [Table 13](#)). Swab samples that are positive by RSV qRT-PCR will be tested by a multiplex PCR (panel of viruses) for detection of potential viral co-infection. Further assessment of samples negative by RSV qRT-PCR may be performed with multiplex PCR if deemed necessary.

**CONFIDENTIAL**208851 (RSV OA=ADJ-002)  
Protocol Amendment 1 Final**Table 13 Molecular Biology (PCR tests)**

Component	Kit / Manufacturer	Method	Unit	Laboratory
System: Nasal/throat swab specimen				
Respiratory Syncytial Virus A RNA Respiratory Syncytial Virus B RNA	In-house	Quantitative RT-PCR	Copies/ml	GSK Biologicals* or designated laboratory
Influenza A virus (Flu A) Influenza B virus (Flu B) Human respiratory syncytial virus A (RSV A) Human respiratory syncytial virus B (RSV B) Human Influenza A virus subtype H1 (Flu A-H1) Human Influenza A virus subtype H3 (Flu A-H3) Human Influenza A virus subtype H1pdm09 (Flu A-H1pdm09) Human adenovirus (AdV) Human metapneumovirus (hMPV) Human enterovirus (HEV) Human parainfluenza virus 1 (PIV1) Human parainfluenza virus 2 (PIV2) Human parainfluenza virus 3 (PIV3) Human parainfluenza virus 4 (PIV4) Human bocavirus 1/2/3/4 (HBoV) Human rhinovirus A/B/C (HRV) Human coronavirus 229E (229E) Human coronavirus NL63 (NL63) Human coronavirus OC43 (OC43)	Allplex Respiratory Panel or alternative	Multiplex PCR	Qualitative assay (positive/negative)	GSK Biologicals* or designated laboratory

Quantitative RT-PCR: quantitative reverse transcription polymerase chain reaction; RSV: respiratory syncytial virus

\* GSK Biologicals laboratory refers to the CLS in Rixensart, Belgium; Wavre, Belgium; Marburg, Germany.

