- *Instructions for assessment visit for suspected respiratory tract infection (RTI): Site staff will decide on the management of the cases (either having a site/different site location/home visit or by telephone contact) based on COVID-19 national guidelines and/or site restrictions linked to the special circumstances. If the nasal and throat samples cannot be collected at site, the sample will be encoded as missing. Samples that are not collected will be documented as protocol deviations. Biological samples will not be collected if they cannot be processed in a timely manner or appropriately stored until the intended use.*

*Impact on the per protocol set for immunogenicity will be determined on a case by case basis.*

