### 8.1. Active surveillance

Active surveillance will only be carried out during the RSV seasons (approximately from October to March) throughout the entire Part B of the study. Study participants will be contacted by the investigator/study staff every 2 weeks to identify if they experience RTI symptoms (e.g., cough, runny nose, fever or difficulty to breath).

In case of RTI symptoms (at least 3) reported by the subject, the subject will be asked to collect a nasal swab at home within 48 hours after the start of symptoms and contact the investigator/study staff, who will schedule an assessment visit for nasal and throat swab specimen collection by qualified staff from the study team. The assessment visit should take place as soon as possible after the start of symptoms (ideally within 48 hours, but no later than 7 days). Episodes should be treated accordingly to local standard of care.

**CONFIDENTIAL**208851 (RSV OA=ADJ-002)  
Protocol Amendment 1 Final

In the event that it is not possible to schedule an assessment visit, the assessment visit page of the eCRF should be filled in as completely as possible using available medical records.

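### Section 10.10 calls a rate limited to visited, swabbed episodes all-cause RTI, and attaches to it a co-infection breakdown that the mandatory testing does not support

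*Protocol*

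**What the plan says.** Protocol Section 10.10 opens with the Exposed Set and then one entry rule: "Any RTI episode for which a visit for the assessment of potential RSV-RTI has been performed (with nasal/throat swab sampling) will be considered". No exception follows. RSV infection is to be assessed separately on subject-collected and staff-collected swabs. After the RSV-RTI proportion and viral load, the section adds: "The incidence rate of all-cause RTI (with 95% CI) will be calculated by group". The next sentence reads: "These will also be presented by co-infection identified by multiplex PCR".

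Other sections record more episodes than this rule admits:
- Sections 5.8.1, 8.1 and 8.2 cover episodes without a visit: "In the event that it is not possible to schedule an assessment visit, the assessment visit page of the eCRF should be filled in", using medical records. Section 8.3 gives every RTI episode its own eCRF number.
- Section 5.10, added by Amendment 1, lets sites manage suspected RTI by telephone and states: "If the nasal and throat samples cannot be collected at site, the sample will be encoded as missing".

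On the virus panel, Section 5.9.3 says: "Swab samples that are positive by RSV qRT-PCR will be tested by a multiplex PCR (panel of viruses) for detection of potential viral co-infection". For the remainder it says: "Further assessment of samples negative by RSV qRT-PCR may be performed with multiplex PCR if deemed necessary". The footnote to Table 17 repeats both rules. Neither place gives a criterion for testing negatives.

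Section 10.3 lists RSV-associated RTI by qRT-PCR in self-collected swabs as a tertiary endpoint. A separate tertiary endpoint covers RSV-associated RTI including co-infections by multiplex PCR.

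**The concern.** An all-cause rate needs only that an episode occurred and was recorded. The protocol arranges for episodes to be recorded when no visit or staff swab is possible, and Section 10.10 then leaves them out. A reader of the report would take the figure as the RTI rate in each group, when it also reflects whether a visit and a swab could be arranged.

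The same rule governs the whole section, so it reaches the self-swab endpoint. A subject may swab at home, test RSV-positive and have no assessment visit. Section 5.10 makes this more likely, since it has subjects store the home swab until they have recovered. Followed literally, Section 10.10 excludes that case from an endpoint defined by the self-swab.

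The co-infection sentence comes directly after the all-cause rate. If it applies to that rate, it asks for a breakdown by a test that is guaranteed for only a subset of the episodes counted.

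**Working it through.** The protocol states no RTI rate, sample size or power for this analysis, so there is no figure to reproduce. The check compares the sections and uses simple proportions.

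**1. Which episodes are counted**

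| Episode | Recorded in eCRF? | Enters Section 10.10? |
|---|---|---|
| Visit held, staff swab taken | Yes (8.3) | Yes |
| No visit possible, page completed from medical records | Yes (5.8.1, 8.1, 8.2) | No |
| Telephone management, staff swab coded missing | Yes (8.3, 5.10) | No |
| RSV-positive self-swab, no assessment visit | Yes (8.3) | No, although the self-swab is the endpoint sample (10.3) |

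Let m be the share of recorded episodes without a swabbed visit. With the same follow-up time in the denominator,

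counted rate = (1 − m) × recorded rate.

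The direction is downward for any m above 0. The protocol gives no value for m. As an illustration only, with assumed values: m = 5% gives 0.95 of the recorded rate, 10% gives 0.90, 20% gives 0.80 and 30% gives 0.70.

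**2. How many counted episodes have a guaranteed panel result**

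Let p be the RSV-positive share of swabbed episodes. The only RSV share in the protocol is in Section 1.1: 7.4% on average, 0% to 17.1% across countries, among adults aged 65 and over with influenza-like illness. It is a proxy here, since the trial's episodes are season-restricted, in ages 60-80, and swabbed on at least three listed symptoms.

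Share with no mandatory panel = 1 − p:
- p = 7.4%: 1 − 0.074 = 92.6%
- p = 17.1%: 1 − 0.171 = 82.9%
- p = 0%: 100%

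For half of swabbed episodes to have a panel result, discretionary testing would have to reach (0.5 − p)/(1 − p) of the RSV-negative swabs:
- p = 7.4%: 0.426/0.926 = 46%
- p = 17.1%: 0.329/0.829 = 40%
- p = 0%: 50%

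**3. What the endpoint asks for**

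The tertiary endpoint in Section 10.3 places co-infection within RSV-associated RTI. Panel testing of RSV-positive swabs is enough for that. It is not enough for a breakdown of all RTI.

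**The case against.** All-cause RTI appears in no objective and no endpoint. It is one descriptive line in a section that Section 10.11 treats as descriptive, and Section 1.2.2 rests formulation selection on safety, reactogenicity and immunogenicity. The secondary endpoint, RSV-RTI by qRT-PCR on assessment-visit swabs, needs a swab by definition. All of this stands and limits the weight of the point.

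Restricting to visited episodes can also be defended on data quality. Qualified staff document signs objectively at the visit, whereas other episodes are completed from whatever records exist. That supports showing the restricted rate, but not calling it all-cause.

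The co-infection sentence begins with a plural pronoun after a singular subject, so it may refer to the RSV-RTI summaries above it. On that reading the mandatory testing suffices. The reading is possible, but the position of the sentence points to the all-cause rate, and the scope should not be left to the reader.

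A reader might infer more than the documents support:
- **That the panel is barred for RSV-negative swabs.** It is discretionary, so a missing panel result for most episodes is the default expectation and not a certainty.
- **That untested episodes will be shown as virus-free.** No text says so, and table handling commonly belongs to the SAP.
- **That the groups will be biased against each other.** Allocation is minimised on center within each step (Section 5.2.2.2.1), so site restrictions should fall roughly evenly.
- **That discretionary testing will be selective by group.** The testing laboratory is blinded to treatment (Section 5.3).
- **That the pandemic removes most episodes.** Surveillance runs about October to March, Amendment 1 is dated 13 May 2020, and home visits remain an option.

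**Conclusion.** The concern holds in a limited form. Section 10.10 applies a visit-and-swab rule to every RTI analysis, so the rate it calls all-cause is understated relative to the episodes recorded, by an amount the protocol does not allow anyone to calculate. The same rule, read literally, removes RSV-positive self-swabs without a visit from the self-swab tertiary endpoint. An all-cause breakdown by panel result is not supported by the mandatory testing: about 93% of swabbed episodes (83% to 100%) would lack a mandatory result if the RSV share in influenza-like illness carries over to this trial.

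The importance is minor to moderate. The rate is descriptive, no formulation decision rests on it, and panel coverage does not affect the staff-swab secondary endpoint.

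**What to change.** Reword Section 10.10 in three places:

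1. Calculate the all-cause RTI rate from all RTI episodes recorded in the eCRF. Show the visited-and-swabbed rate beside it, and report the number of unswabbed episodes by group.
2. Limit the co-infection breakdown to RSV-positive RTIs, in line with the tertiary endpoint in Section 10.3.
3. Apply the visit-and-staff-swab restriction only to the staff-swab secondary endpoint, so that the self-swab endpoint counts a positive self-swab without an assessment visit.

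The cost is wording in one section and one extra table from data already collected, with no new samples or assays. The downside is that episodes completed from medical records are less uniformly ascertained. Reporting both rates lets the reader see how much that matters.
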